4.4 Patient Analysis Sets

All subjects that are randomized at Study Visit 1 (baseline visit) are considered study participants. The following study populations and analysis sets will be defined:

Safety Population: This will include all subjects that are randomized to, and receive, one of the trial treatments.

Full Analysis Set: Using the Intent-to-treat (ITT) principle, this will include all subjects that are randomized and receive trial treatment, and attend at least one follow-up post baseline. Subjects will be analyzed according to treatment randomization.

Per Protocol Population (PP): This will include all subjects that are randomized to trial treatment, meet the inclusion/exclusion criteria, do not discontinue treatment within the first nine (9) weeks (- 1 day) and have no significant protocol deviations. Subjects that achieve closure will be included regardless of time on therapy unless they are deemed to have significant protocol deviations or failed to meet the inclusion/exclusion criteria.

Statistical analysis will be performed using each of the subject populations as follows. Analysis of the primary, secondary and exploratory efficacy objectives will be performed separately using both the Full Analysis Set and the Per Protocol Population. All safety analyses will utilize the Safety Population.

The numbers of subjects in each analysis data set will be summarized and listings of patients excluded from each analysis set along with the reasons for exclusion will be provided.

4.5 Disposition of Patients

The numbers of subjects that are screened, the number of subjects that enter the study (i.e. are randomized) and the number of subjects that attend Study Visit 2-14 will be summarized.

ST:

9 7 5

Reference:

CE/052/PIC

Customer Code:

0 5

The screening duration will be summarised for all subjects separately for screening period, re-screening period 1 and re-screening period 2, and overall. The number of screening periods (including any re-screen periods) per subject will also be summarised.

The reasons for study completion and withdrawal will be summarised. The study duration will be summarised by reason for study completion and overall.

Details of the dates that the first subject was screened, first subject randomized and the last patient completed will be provided.

4.6 Protocol Deviations

The occurrence of the following examples of protocol deviations and significant protocol deviations, and the number of subjects with a protocol deviation and significant protocol deviation will be summarized:

- Patients that do not meet the inclusion/exclusion criteria but are randomized (the reason for failure of inclusion/exclusion criteria will be summarized)
- Subjects with a PICO duration of dressing wear is >7 days where no wound filler is used
- Subjects with an ActiV.A.C.®, or PICO in combination with a wound filler, with a duration of dressing wear >3 days
- Missed Study Visit

- Patients that receive study treatment with NPWT for greater than 85 days (12 weeks allowing +1 day)
- Patients taking a prohibited concomitant medication
- Patients with a serious device related adverse event who are not withdrawn from study treatment
- Attendance of weekly Study Visit outside ± 1 day window
- Failure to complete the Subject Exit survey or Health Related Quality of Life questionnaires (EQ-5D or CWIS) at the required timepoints

Document Number: 1004313

Document Part: 000

Document Version: 06

Document Status: Released

4.7 Measurement of Treatment Compliance

The number of treatment applications per subject will be summarized. In addition, subject attendance at each Study Visit will be summarized.

4.8 Baseline Data

Demographics

Patient demographics including age, gender, height, weight and body mass index (BMI) will be summarised. Race and Ethnicity will also be summarized.

Medical History

Relevant medical history (presence/absence of relevant medical conditions and duration since onset), diabetes status, and type of diabetes will be summarized.

Smoking status and patient mobility will be summarized.

Reference ulcer details

Reference ulcer type including grade of Diabetic Foot Ulcers will be summarised.

The side and location of the reference wound, the duration of the reference wound, how many ulcers are on the target leg, whether the ulcer has ever healed and recurred, and arterial supply measurements (ABI, GTP, TcPO2, and waveform pattern) will be summarized.

Whether the target ulcer has had any previous treatment, if so the products used, including the duration of NPWT, type of compression and type of offloading therapy will be summarized. The dressings applied for the duration of the screening run-in period will be summarized. The intended method of ulcer closure will also be summarized.

Reference ulcer dimensions at Run-In Visit 2 (baseline) including area, perimeter, depth and volume will be summarised. In addition the change and percentage change in reference ulcer dimensions during the Screening/Run-In period will be summarized.

Homogeneity of treatment groups

Individual two-sample t-tests will be used to test for a difference in the means of the following baseline characteristics between treatment sequence groups separately for each wound type (VLU/DFU) and overall: patient age, BMI, baseline wound area, wound duration and level of wound pain recorded during Screening Run-In Visit 1. If the assumptions of the t-test are violated, Wilcoxon rank sum test will be used instead with median Hodges-Lehmann estimates of the differences reported.

Individual Cochran-Mantel-Haenszel tests will be used to test for a difference in the following baseline characteristics between treatment sequence groups separately for each wound type (VLU/DFU) and overall: level of exudate.

4.9 Primary Variable

The primary objective of the study is to compare PICO against ActiV.A.C.® in terms of the percentage change in the target ulcer area, over the 12-week treatment period.

Primary Analysis

An initial linear regression model will contain covariates for treatment, center, wound type, baseline (defined as Run-In Visit 2/Study Visit 1) target ulcer area and duration of target ulcer. For purposes of the primary analysis, any centers with less than 10 subjects will be pooled. A forward selection procedure will be used for the addition of other baseline covariates with an F-value to attain a significance level of 0.1. Further baseline covariates to be assessed as part of this procedure include: subject age, body mass index, baseline ulcer depth, ABI and baseline level of exudate. The resulting primary analysis presented will correspond to the final model from the forward selection procedure. The results for the initial model will also be presented. For each of the effects in the initial and final model, the p-value, parameter estimate and corresponding 95.4% confidence interval will be presented.

Non-inferiority will be concluded if the upper bound of the 95.4% confidence interval for the parameter estimate relating to treatment covariate (coded as ActiV.A.C.® – PICO) is less than ($<$) 12.5 which relates to the desired one-sided test at the 2.5% significance level after adjusting for the interim analysis.

If distributional and model assumptions relating to the above analysis do not hold, a permutation test will be used as a non-parametric non-inferiority analysis. The sampling distribution of the test statistic will be estimated by re-randomization of treatments to each of the study subjects. At a minimum the completed re-randomization process will be repeated 2000 times. However, if 2000 replicates are found to be insufficient for the random variation in results of successive repeats to be reduced to an acceptable level, the number of replicates will be increased until such a point as consistent results are observed between successive repeats of the permutation tests up to a maximum of 10,000 replicates.

For purposes of the permutation analysis, to test against the null one-sided hypothesis of a difference greater than delta, the non-inferiority margin (delta=12.5%) will be added to, or subtracted from, the observed change in individual area measurement for those subjects that are re-randomized by the permutation test to the treatment which they were not randomized to during the trial. The resulting p-value will be derived as per usual bootstrapping techniques.

The primary analysis will be performed using the Per Protocol Population; the analysis will also be repeated using the Full Analysis Set. Differences in conclusions between the two analyses will be investigated. The ability to switch between non-inferiority and superiority will be considered only if both subject populations demonstrate non-inferiority.

Secondary Analysis

Secondary subgroup analyses may be conducted as a result of the covariate analyses. Additionally, treatment will be fitted on its own in a further linear regression model. The potential for interactions, particularly treatment by center interactions will be examined by fitting the required interaction terms in addition to those effects in the final linear regression model from the forward selection procedure.

The baseline area, final area, absolute change in area and percentage change in ulcer area over the 12-week treatment period will be summarized separated by treatment, centre, wound type and area used for stratification purposes (large/small) and baseline area (<median/>=median). Further summaries will be produced separated by the covariates used in the final model. The ulcer area, change in area and percentage change in area will be summarized by Study Visit (2-12) and

treatment, centre, wound type and area used for stratification purposes (large/small). Summaries will utilize the Per Protocol Population and will be repeated for the Full Analysis Set.

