2. STUDY DESIGN

2.1 DESCRIPTION OF TRIAL DESIGN

This is a multi-center, Phase 4, randomized, open-labelled, comparative-effectiveness study in subjects with at least one lower extremity wound (VLU or DFU). Subjects will be randomized to one of two treatment groups to receive either PICO single-use NPWT system or ActiV.A.C. ® System, for 12 weeks, or until target ulcer closure (by surgical intervention or secondary intention), whichever occurs first.

The study consists of four periods: a 1-week run-in period (including screening Run-In Visit 1, Run-In Visit 2), a 12-week randomized treatment period (including Study Visit 1 through Study Visit 12), a 1-week end-of-treatment assessment period (including Study Visits 13, 14). Study Visit 14 serves as the end of study visit.

Following a 1-week run-in period, approximately 160 subjects meeting entry criteria will be randomly assigned to one of the two treatment arms in a 1:1 allocation ratio to receive treatment with either PICO single-use NPWT system or ActiV.A.C. ® system for 12 weeks with dressing changes as deemed required in the opinion of the investigator or required in the instructions for use (IFU).

Eligible subjects will receive treatment for 12 weeks (Visits 1 through 12), or until their wound closes or progressing sufficiently to become ready for surgical closure in the opinion of the investigator. Subjects whose wounds have closed, as assessed by the Investigator, prior to the 12th week of treatment (or Visit 12) will stop treatment and return for one further visit (Visit 14) to verify if the target ulcer remains closed for one week following the initial observation of ulcer closure. An ulcer which remains closed at this one week verification assessment is defined as having achieved complete wound closure in this study.

For those subjects who are randomized and who discontinue from the study prior to Visit 13 due to any reasons other than target wound closure, Visit 14 will serve as the early termination (ET) visit.

The size of the target ulcer, pain associated with target ulcer will be assessed for each subject at Run-In Visit 1 (screening). This information, along with the status of

Document Number: 1004313
Document Version: 06

Document Part: 000
Document Status: Released

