3. STATISTICAL CONSIDERATIONS

3.1 DETERMINATION OF SAMPLE SIZE

The study is intended to test for non-inferiority in the percentage change in target ulcer area between PICO and tNPWT over a 12-week treatment period. During a review of five previous studies with venous leg ulcer and diabetic foot ulcer, with treatment of PICO or tNPWT, the mean percentage change in ulcer area was found to be approximately between 47-62%, in cases where it was considered an appropriate measure, the standard deviation ranged approximately between 21-24.5%. Using a non-inferiority margin of 12.5%, a sample size of 128 subjects will provide 80% statistical power at the (cumulative) 0.025 one-sided significance level assuming a weighted average mean healing of 60% with a worst case standard deviation of 24.5%. This was calculated using EAST 6. To allow for a 20% drop out rate throughout the 12-week treatment period, a total of approximately 160 subjects (80 per treatment) will be randomized.

The sample size randomized will include a minimum of 100 VLU to allow for a minimum of 70% power for VLU-only analysis using the above assumptions.

An interim analysis (built into the sample size) of key variables will take place after approximately 50% of target recruitment (80 subjects completed) with the stipulation that the interim will contain at least 40 VLU and 20 DFU. A recommendation may be made at this point to stop the trial prematurely due to efficacy or futility.

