3.2 RANDOMIZATION

All eligible subjects will be randomized between PICO and ActiV.A.C.[®] therapy settings by means of an online randomisation system (Sealed Envelope).

Treatment will be randomized, stratified by wound type and wound size at the conclusion of the screening period (and prior to commencement of the treatment period) to prevent imbalance on these variables between the two treatment groups.

The resulting strata will be as follows:

- *Small DFU ($\leq 2 \text{ cm}^2$)*
- *Large DFU ($> 2 \text{ cm}^2$)*
- *Small VLU ($\leq 12 \text{ cm}^2$)*

- Large VLU (>12 cm²)

A blocked randomization will be used for each stratum utilizing a block size of 2 and 4. Due to visible differences between treatments, allocation to treatment will not be blinded.

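### The initial linear models omit the type-by-size randomization strata; ulcer size drops out of the depth and volume models altogether, while the primary area model loses little

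*SAP*

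**What the plan says.** SAP 3.2 sets out the allocation: "Treatment will be randomized, stratified by wound type and wound size at the conclusion of the screening period". There are four strata: DFU up to or above 2 cm², and VLU up to or above 12 cm², with blocks of 2 and 4 in each. Protocol 8.1 gives the same strata and makes the meaning of small and large depend on ulcer type.

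SAP 4.9 gives the model for the main endpoint: "An initial linear regression model will contain covariates for treatment, center, wound type, baseline (defined as Run-In Visit 2/Study Visit 1) target ulcer area". The one remaining term is how long the ulcer has been present. Protocol 10.3.1 lists the same terms. The forward-selection candidates are age, BMI, baseline depth, ABI and exudate level. Neither the size class nor a type-by-area term appears in either list. For the primary variable the large/small class is used only to split descriptive summaries.

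SAP 4.10 repeats this analysis for depth and volume with one change: baseline depth or volume takes the place of baseline area.

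**The concern.** When allocation is balanced within strata that predict outcome, the treatment estimate is more precise than a model without those strata reports. The reported standard error is then too large and the design's gain is lost.

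The strata treat size as relative to type: a 4 cm² ulcer is large for a DFU and small for a VLU. The eligible ranges also differ, at 0.5–10 cm² for DFU and 2–36 cm² for VLU (Protocol 7.2). The primary model assumes the same effect per cm² in both types, and the plan does not justify this. The depth and volume models contain no area term. What is at stake is the width of the confidence intervals, mainly for the two key secondary endpoints.

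**Working it through.** **1. The plan's own sample size.** SAP 3.1 gives these inputs: "Using a non-inferiority margin of 12.5" (per cent), "worst case standard deviation of 24.5" (per cent), a common mean ("assuming a weighted average mean healing of 60" per cent, so a true difference of zero) and 1:1 allocation.

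- Fixed design: n per arm = 2(1.960 + 0.842)² × 24.5² / 12.5² = 60.3, rounded up to 61, or 122 in total.
- With the interim look (efficacy Z 2.963, futility Z 0.559 obeyed, information 0.5, final critical value 1.969 to hold one-sided 0.025), power at 64 per arm is 80.2%. The statement that "a sample size of 128 subjects will provide 80% statistical power at the (cumulative) 0.025 one-sided significance level" is reproduced.
- 128 / 0.8 = 160 randomized.

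The SD of 24.5 is not reduced for covariates. The planning standard error is 24.5 × √(2/64) = 4.33, and the 80% relies on no adjustment for size.

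**2. Where size enters each model.**

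| Model | Wound type | Size information |
|---|---|---|
| Area (SAP 4.9) | yes | continuous area, one slope for both types |
| Depth (SAP 4.10) | yes | none |
| Volume (SAP 4.10) | yes | only through baseline volume |

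**3. Depth model.** Let size explain a share R² of outcome variance, and let the strata capture a fraction k of that share. If baseline depth is unrelated to area, the planned standard error divided by the one with strata is about 1/√(1 − kR²).

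- Step at the cuts: k = 1.
- Smooth effect in log area, areas log-uniform over the eligible range: k = 3p(1 − p), where p is the fraction below the cut.
  - VLU: p = ln(12/2)/ln(36/2) = 0.620, k = 0.707.
  - DFU: p = ln(2/0.5)/ln(10/0.5) = 0.463, k = 0.746.
  - Weighted 88 VLU to 40 DFU: k = 0.719.

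The table shows how much larger the planned standard error is. The simulation used 1,500 trials per case, N = 128, blocks of 2 and 4 in four strata, eight centers, and duration left out.

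| Effect of size | R² 5% | 15% | 30% |
|---|---|---|---|
| Smooth, formula | 1.8% | 5.9% | 12.9% |
| Smooth, simulated | 1.8% | 5.8% | 13.1% |
| Smooth, depth–area correlation 0.5 | 1.1% | 4.0% | 9.2% |
| Step, formula | 2.6% | 8.5% | 19.5% |
| Step, simulated | 2.6% | 8.6% | 20.0% |
| Step, depth–area correlation 0.5 | 2.0% | 7.1% | 16.6% |

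With no size effect, adding the strata costs about 0.1%. At R² = 30% the two-sided error of the 95.4% interval falls to 0.025–0.035 against a nominal 0.046. With strata it is 0.045–0.055 (Monte Carlo error about 0.005).

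**4. Primary area model.** Ratio of the planned standard error to that with strata added, on the same layout:

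| Area–outcome relation | R² 5% | 15% | 30% |
|---|---|---|---|
| Linear, common slope | 0.997 | 0.997 | 0.996 |
| Linear in log area | 0.999 | 1.005 | 1.016 |
| Same standardized slope in each type | 0.999 | 1.005 | 1.016 |
| Opposite slopes by type | 1.004 | 1.022 | 1.052 |
| Step at the cuts | 1.007 | 1.031 | 1.078 |

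Further runs of the smooth log-area case reached 2.6%. In patients, 1.016² − 1 = 3.2%, or about 4 of 128; 1.078² − 1 = 16.2%, or about 20. Power changes by −0.7 to +1.0 points in the smooth same-direction cases, and by +3.5 points (87.5% to 91.0%) in the strongest step case. In that last case the planned model's one-sided error is 0.015 against a nominal 0.023 (Monte Carlo error about 0.004).

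**The case against.** For the primary endpoint the plan has a good answer. Wound type is in the model, and size enters as measured area, which usually carries more information than a two-level class. With an intercept for type, a common slope does represent size within type; it only assumes the same effect per cm². The clear gains need a jump exactly at 2 and 12 cm², the shape a stratum indicator fits perfectly, or slopes of opposite sign. A 20-point jump with half the ulcers on each side explains 10²/24.5² = 17% of variance and is worth about 3% in standard error. Nothing in the documents supports such a jump. All of this stands.

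A separate area slope for each type also did as well as or better than the strata in every case except the step, so the strata are not the only remedy for area.

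The objection does not carry over to depth and volume, where the area term has been taken out. It has some force for volume, since baseline volume itself reflects area; only the depth model was simulated.

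For the logistic and Cox closure models no gain was shown. With as few as 46 DFU randomized, the split DFU strata may be sparse, and added covariates change the conditional odds or hazard ratio being estimated.

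**Conclusion.** This is a minor point that holds mainly for the key secondary endpoints. In the depth model the size factor used to randomize is missing, and the standard error is about 1–13% too large for a smooth size effect and 2–20% for a step, if size explains 5–30% of variance. The volume model has the same gap, probably smaller. In the primary area model, adding the strata ranges from about 0.4% worse, through 0–3% better for smooth same-direction effects, to a planned standard error about 5% (opposite slopes) or 8% (strong step) too large.

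These figures rest on assumptions outside the documents: the variance share, the shape of the effect, log-uniform areas, 88 VLU and 40 DFU, and eight pooled centers.

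A reader might infer three stronger things that the documents do not support:

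- That the primary analysis gives up precision at no cost. If outcome is linear in area with a common slope, or unrelated to area, the strata make the standard error slightly worse.
- That the trial falls short of its 80% power. That figure uses an unadjusted SD.
- That a false claim of non-inferiority becomes more likely. Where the omission matters, it makes the test conservative.

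**What to change.** In SAP 4.9 and in the depth and volume part of 4.10, replace wound type by the four-level randomization stratum in the initial linear models, and keep the continuous baseline measurement (area, depth or volume). For area alone, a type-by-area term is an acceptable alternative. Align Protocol 10.3.1 and 10.3.2, which carry the same model terms. If the strata are left out, give the reason.

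Use the stratum as recorded in the randomization system, and reconcile which area defines it. Protocol 8.1 says size at baseline, Protocol 9.1.3 says size seen at the screening visit, and SAP 3.2 says the conclusion of screening. Both run-in visits carry the word screening in their titles, so the second could mean either one.

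Extending the change to the closure models is optional.

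The cost is wording and two degrees of freedom: at most about 0.4% in standard error for area, and about 0.1% for depth, if size turns out not to matter.

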If debridement is not performed, an image of the target ulcer is still required to determine the ulcer area (cm²), perimeter (cm), greatest depth (mm), volume (cm³) and maximum linear dimension (cm) using the ARANZ Silhouette wound imaging and measurement device. This is the baseline ulcer assessment measurement.

Calculate the percent change in ulcer area.

$$\Delta = \frac{Area_{RV2} - Area_{RV1}}{Area_{RV1}} \times 100\%$$

If (Δ) percent change \geq 30% decrease in target ulcer area; subject will be excluded from randomization and participation in the study.

9.1.3 Randomization Study Visit 1

This visit is a continuation of Screening Run-in Visit 2 for all eligible subjects and should be completed on the same day.

Upon completion of all Screening Run-in Visit 2 procedures and confirmation that the subject is eligible for the study, the Investigator or designee will register the subject using an electronic randomization system to calculate the percent change in the target ulcer. If the subject's percent change meets the eligibility criteria the subject will be randomized and then will enroll into the treatment period of the study. The randomization will be stratified based on target ulcer size and wound type observed at the screening visit. The details of the stratification factors and the process of the stratified randomization will be provided in the SAP. The subject will then receive the study treatment allocated to that subject identification number per instructions received from the electronic randomization system. Then the following procedures will be completed:

1. Subjects will be randomized using an electronic randomization system (www.sealedenvelope.com) to either treatment with PICO or tNPWT systems, and assigned a subject randomization number.
2. Conduct an ulcer assessment using the modified Bates-Jensen wound assessment

CONFIDENTIAL DOCUMENT
This document contains confidential information, which is the property of Smith & Nephew, Inc. Do not copy, disclose, or circulate without written authorization from the appropriate Smith & Nephew personnel

tool and record percentage tissue type/condition of peri-wound skin assessment (Normal, Erythematous, Edematous, Eczematous, Excoriated, Macerated, Indurated).

3. Ask the subject to complete the Cardiff Wound Impact Schedule (CWIS) quality of life questionnaire and EQ-5D.
4. Application of investigational product (PICO) or comparator tNPWT system according to randomization schedule.

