15. The change in target ulcer area during the screening period will be derived as (change in depth and volume will be derived using the same method):

$$Area_{Run-In\ 2} - Area_{Run-In\ 1}$$

16. The percentage change in target ulcer area during the screening period will be derived as (percentage change in depth and volume will be derived using the same method):

$$\left(\frac{Area_{Run-In\ 2} - Area_{Run-In\ 1}}{Area_{Run-In\ 1}} \right) \times 100$$

17. Target ulcer area is defined as surface area as measured by the ARANZ Silhouette Device at each study visit by the Investigator. For each study visit, the change in target ulcer area will be derived as (change in depth and volume will be derived using the same method):

$$\text{Change in target ulcer area at Study Visit } n = Area_{SVn} - Area_{SV1}$$

18. For each study visit, the percentage change in target ulcer area will be derived as (percentage change in depth and volume will be derived using the same method):

$$\text{Percentage change in target ulcer area at Study Visit } n = \left(\frac{Area_{SVn} - Area_{SV1}}{Area_{SV1}} \right) \times 100$$

For purposes of the primary analysis, the percentage change in target ulcer area will be derived as using LOCF within the 12-week treatment period. The percentage change in depth and volume will be derived using the same method.

19. The time to achieve confirmed ulcer closure in days will be derived as follows:
- For those subjects that achieve confirmed closure (derived variable 20):
Date of Study Visit where closure is first recorded – Date of Randomization
 - For those subjects that achieve closure but do not achieve confirmation (derived variable 20):
Date of Study Visit where closure is first recorded – Date of Randomization
 - For those subjects that do not achieve closure during the 12-week treatment period or withdraw early, the time to achieve confirmed ulcer closure will be defined as either: Date of last study visit attended – Date of Randomization;
Or 84 days, whichever occurs earlier.

20. Whether confirmed ulcer closure was achieved will be derived as follows:

- Ulcer Closed/Ready for surgical closure=Yes at last attended Study Visit i, Ulcer Closed=Yes at Follow up assessment (Visit 14). Confirmed Closure = Yes
- Ulcer Closed/Ready for surgical closure =Yes at last attended Study Visit i, Ulcer Closed=No at Follow up assessment (Visit 14). Confirmed Closure = No

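### The primary model omits the run-in percentage change in ulcer area, a pre-randomization value that every randomized subject has, so some precision is probably given up

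*SAP*

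**What the plan says.** The primary analysis (SAP 4.9, Protocol 10.3.1) is a linear regression of percentage change in target ulcer area. Five terms are fixed: treatment, center, wound type, baseline area and ulcer duration. Others may enter by forward selection at the 0.1 level: "Further baseline covariates to be assessed as part of this procedure include: subject age, body mass index, baseline ulcer depth, ABI", and baseline exudate level.

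The run-in change in area appears elsewhere in the plan:

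- **Eligibility.** Protocol 7.3.1 excludes a subject whose ulcer shrinks by 30% or more during the run-in. Under Protocol 9.1.3 the electronic randomization system calculates the change: "If the subject's percent change meets the eligibility criteria the subject will be randomized".
- **Derivation.** SAP 4.3 item 16 reads "The percentage change in target ulcer area during the screening period will be derived as", followed by the formula. It adds that depth and volume are handled in the same way.
- **Use.** SAP 4.8 says "the change and percentage change in reference ulcer dimensions during the Screening/Run-In period will be summarized". I found no other analysis that uses it. It is not a stratification factor (SAP 3.2) and is not among the baseline homogeneity tests (SAP 4.8).

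The depth and volume models repeat the primary analysis with their own baseline value in place of area. The logistic closure model and the proportional hazards model (SAP 4.10, Protocol 10.3.2) also omit the run-in change.

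**The concern.** The plan treats one week of healing as informative enough to bar fast healers. It then lets age, body mass index and ABI compete for a place in the primary model, but not this variable. Run-in change is the only value measured before randomization that is on the same scale as the primary endpoint, and the randomization system needs it to admit a subject, so it should be present for everyone randomized.

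If it predicts the 12-week change beyond the terms already fixed, leaving it out keeps avoidable residual variance in the 95.4% interval that is compared with the 12.5-point margin. At stake is extra power and a somewhat narrower interval, obtained without new visits or measurements.

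**Working it through.** **Inputs (SAP 3.1, 2.1, 3.3, 4.9).**

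- Margin: "Using a non-inferiority margin of 12.5" percentage points.
- Mean and SD: "assuming a weighted average mean healing of 60% with a worst case standard deviation of 24.5". The same mean in both arms gives a true difference of 0.
- Target: "a sample size of 128 subjects will provide 80% statistical power at the (cumulative) 0.025 one-sided significance level", "in a 1:1 allocation ratio".
- Interim at about half: efficacy bound Z 2.963, non-binding futility bound Z 0.559. Final interval 95.4%.
- Partial correlation r of run-in change with the 12-week change, given the other covariates: **not in the documents**, so a range is assumed.

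**Step 1: reproduce the plan.** A fixed design needs 2 × 24.5² × (1.960 + 0.842)² / 12.5² = 60.3, so 61 per arm or 122 in total. That is short of 128 because the interim is built in. With two looks at information 0.5 and futility non-binding, the final bound for one-sided 0.025 is Z = 1.969. The final drift is 12.5 / (24.5 × √(4/128)) = 12.5 / 4.331 = 2.886. Power is P(Z₁ > 2.963) + P(0.559 < Z₁ < 2.963, Z₂ > 1.969) = 80.2%. Dropout gives 128 / 0.8 = 160. The plan's figures reproduce.

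**Step 2: add the covariate.** Residual SD = 24.5 × √(1 − r²). Interval half-width = 1.995 × residual SD × √(4/128).

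| r | Variance removed | Residual SD | Drift | Power at 128 | Half-width | Completers for the same power as r = 0 |
|---|---|---|---|---|---|---|
| 0 | 0% | 24.50 | 2.886 | 80.2% | 8.64 | 128 |
| 0.1 | 1% | 24.38 | 2.901 | 80.6% | 8.60 | 128 |
| 0.2 | 4% | 24.00 | 2.946 | 81.8% | 8.47 | 124 |
| 0.3 | 9% | 23.37 | 3.026 | 83.7% | 8.24 | 118 |
| 0.4 | 16% | 22.45 | 3.149 | 86.5% | 7.92 | 108 |

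**Step 3: test the starting SD.** The table applies a partial correlation to the planning SD, as if the five fixed terms explained nothing. If they explained 20% of the variance (an assumption), the SD would be 24.5 × √0.8 = 21.91 and power would start at 88.1%. It would then rise to 89.3% at r = 0.2 and 90.8% at r = 0.3. The gains are 1.2 and 2.7 points, against 1.6 and 3.5 points from the table (81.8 − 80.2 and 83.7 − 80.2).

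**Step 4: which r is plausible.** Two features of the design pull r down.

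- *Range restriction.* With run-in change assumed normal (mean −5% to −15%, SD 15% to 25%), excluding shrinkage of 30% or more lowers a correlation of 0.3 to about 0.22–0.27, and 0.4 to about 0.30–0.37.
- *Shared measurement.* The Run-in Visit 2 area is the end point of the run-in change and the denominator of the endpoint. If it is read too high, run-in shrinkage looks smaller and later shrinkage looks larger, which opposes a true positive association. As an illustration, assume run-in mean −10% and SD 15%, outcome mean −60% and SD 24.5%, a true correlation of 0.3, and the exclusion applied. The observed correlation is then 0.26 with no measurement error, 0.20 with 5% error, 0.10 with 10%, and about 0 with 15%.

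**The case against.** The strongest reply is that no defect has been shown. Leaving out a prognostic baseline covariate does not bias a randomized comparison or raise type I error. The sample size uses the full SD of 24.5 with no stated reduction for covariates, and which further covariates to adjust for is partly a matter of judgment. The variable is also less close to the outcome than it looks. It covers 7 ± 1 days under run-in dressings, with compression for VLU, and not under NPWT. Both areas are measured after any debridement, which at Run-in Visit 2 is at the investigator's discretion, so the change mixes debridement with healing. The exclusion and the shared measurement weaken it further, and at r = 0.1 the gain is 0.4 power points.

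Most of this stands, and it limits the size of the point. It does not remove the case for adding the variable. A linear model gains from r² whatever its sign, so the gain disappears only if the true association is negligible or the opposing effects nearly cancel. The downside is one degree of freedom. A covariate fixed in advance also adds no further data-driven choice to the forward selection.

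**Conclusion.** The omission is confirmed in both documents. Its consequence is a likely, but not certain, loss of precision in the primary linear model. The gain is 0.4 to 6.3 power points for r from 0.1 to 0.4. The lower part of that range is more plausible, and the gain is smaller still if the fixed terms already explain variance. These figures rest on the assumed r, on an interim at half the information and on the planning SD. The change is worth making but is not a condition of validity.

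A reader might infer more than the documents support:

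- *That the trial is underpowered or biased by the omission.* It is not. The stated 80% is reached without the covariate. Chance imbalance in early healing would move the estimate only in proportion to an unknown slope, and the confidence interval already allows for it.
- *That the gain is assured.* No correlation is given, and the design itself offers reasons to expect a small one.
- *That the closure analyses lose precision in the same way.* Residual-variance reasoning belongs to linear models. In logistic and proportional hazards models, adjustment does not normally narrow the interval for the log odds ratio or log hazard ratio. It moves the conditional estimate away from the null and may raise power.
- *That area change suits every model.* For depth and volume, the matching covariate is the run-in change in that same dimension.

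**What to change.** Before any comparative data are seen, the interim included:

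1. In SAP 4.9 and Protocol 10.3.1, name run-in percentage change in area (SAP 4.3 item 16) as a fixed covariate in the initial primary model, not as another forward-selection candidate.
2. In the key secondary models (SAP 4.10, Protocol 10.3.2), use the run-in percentage change in depth or volume, as appropriate. Item 16 already provides for both.
3. Optionally, add the run-in change in area to the closure and time-to-closure models, stating that the aim is power for the conditional effect.
4. State that a re-screened subject contributes the last screening period, in line with SAP 4.1.

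The cost is one degree of freedom per model and a few lines of text, with no new data. The area value should be complete, because randomization depends on it. Depth and volume changes are not needed for randomization, so give a short rule for a missing value.
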